Recruitment via social media. We will recruit participants through a targeted social media advertisement campaign. Recruitment through social media offers the advantage of being able to reach veterans outside the VA system and immediately deliver an online intervention.

We will use Facebook as our primary platform for recruitment; however, in consultation with our partners including the Oregon Health and Science University (OHSU) Strategic Communications social media team, we may include advertisements on other platforms for which they have extensive experience running campaigns (e.g., Instagram). Following a procedure developed in our previous research,³⁶ we will set ads to be presented to Facebook users likely to fit our eligibility criteria. Examples of characteristics we will use include: age, military-related interests or behaviors (e.g., making a charitable donation to a Veteran service organization, listing the military as their industry or employer), and “liking” Facebook pages related to Veterans, suicide prevention, or related topics. Ads will be placed in users’ “News Feeds” and optimized for computer and mobile devices. To assure that sensitive information is not sent in an unencrypted email, these ads will not invite communication from participants. From these feeds, participants will click on the ad and be taken to screening and consent in OHSU REDCap to enter the survey. Ad performance will be monitored in real-time, allowing the potential to retain only the most cost-effective ads in the campaign. The research team will collaborate closely with the OHSU Strategic Communications Social Media team to host ads, and monitor, audit and report on interval progress of the communication campaign. OHSU REDCap captures and stores the number of screened and consented participants and stores this information; we will be able to view and monitor recruitment progress by logging into REDCap and checking these numbers.

Based on our preliminary work recruiting Iraq/Afghanistan-era veterans, budget for recruitment, and empirical data on the slower pace of recruitment for web-based intervention studies that include close supports as participants,^{34, 49} we estimate a 10-week recruitment period to meet our target enrollment of 200 participants (20 participants/week).

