Sample Size Considerations. We first consider whether our proposed sample size (n=200) is sufficient to meet our proposed benchmarks for the proportion of individuals who enroll in the study and loss to follow-up. For the primary analyses in Aim 1, we calculate CI's for a single proportion to determine whether the target benchmarks are within or beyond the CI's. Correspondingly, we used a confidence approach to determine whether our proposed sample size is sufficient to meet our proposed benchmarks.⁶⁸ **Hypothesis 1.2** is that at least 50% of eligible individuals will enroll in the study. Assuming that 357 people are eligible for the study, and 56% enroll (resulting in a sample size of 200 participants), this will give a 95% binomial exact confidence interval of 50.7% to 61.2%. The lower bound of this CI does not overlap with our threshold for an enrollment rate > 50%. For numbers as low as 300 people eligible for the study, a study enrollment rate of at least 56% would be adequate, and with 400 people eligible we would only need 55% to enroll. The **Hypothesis 1.3** benchmark for loss to follow-up at end of study is < 50%. Assuming that the study loss to follow-up rate is 42%, a sample size of 200 gives a 95% binomial exact confidence interval of 35.1% to 49.2%. The upper bound of this CI does not overlap with our 50% threshold for loss to follow-up. For a sample size as low as 150, we would also need a loss to follow-up rate of at most 40%, and with 250 we would need the rate to be at most 42%.

Aim 2's hypothesis is that participants will complete on average at least 70% of the PsychArmor S.A.V.E. training. Since this hypothesis is restricted to the treatment arm, our proposed sample size is 100.

Assuming that the mean percentage of time spent on the training is 73% with a standard deviation (SD) of 15%, a sample size of 100 gives a 95% t-distribution confidence interval of 70.02% to 75.98%. The lower bound of this CI does not overlap with our minimum threshold of 70% completion of the training. For a sample size as low as 75, we would need a mean of at least 74% with SD = 15% and at least 76% with SD = 25%.

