intervention is delivered in English, having already been exposed to the intervention, or misrepresenting their Veteran status.

Table 3: Eligibility Criteria

Inclusion Criteria	Exclusion Criteria
1a) Veteran who has served on active duty in the U.S. Armed Forces within the prior 12 months, or 1b) family member or friend of a Veteran	1) lack a U.S. phone number, email, or computer access 2) not fluent in English 3) have previously taken or intend to take PsychArmor S.A.V.E. training (to minimize contamination of the control group) 4) duplicate study entry or misrepresentation of Veteran status. ⁷³
2) social contact with a Veteran at least weekly	

Number of Participants. In order to obtain a final study sample of 200 participants (half randomized to the intervention and half to the control condition), we anticipate consenting and enrolling a higher number of participants as shown below:

Number of intervention group participants consented: 400

Number of participants enrolled (assumes 50% enroll): 200

Number of participants analyzed (assumes 50% lost to follow-up): 100

Number of control group participants consented: 400

Number of participants enrolled (assumes 50% enroll): 200

Number of participants analyzed (assumes 50% lost to follow-up): 100

Number of total participants consented: 800

Number of total participants enrolled (assumes 50% enroll): 400

Number of total participants analyzed (assumes 50% lost to follow-up): 200

Exclusion of Children. In addition to the above exclusion criteria, we will also exclude children under age 18 years. Children would not qualify as Veterans and would typically not be considered a close support to Veterans due to their young age. The primary focus of this study is looking at the outreach and uptake of online training in an adult population that can be difficult to reach through other means (for example, Veterans that don't use VHA services for their health care) and are at risk of depression and suicide. Although children can suffer from depression and suicide, the proposed methods of this study (an online platform) may not adequately address the sensitive nature of working with children under 18 that are at risk for suicide. Additionally, the military-focused gatekeeper training contained in this study has not been studied or tailored to a younger audience.

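### The case that n = 200 is sufficient shows only that the 95% CI clears each benchmark at an assumed value almost on the pass limit; if those values are true, the chance of clearing is about 60%, 59% and 51%, and the enrolled number (200 or 400) is not settled

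*Combined protocol and SAP*

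**What the plan says.** Sample Size Considerations asks whether 200 participants are enough for the enrollment and retention benchmarks and states the method: "we used a confidence approach to determine whether our proposed sample size is sufficient to meet our proposed benchmarks". The Aim 1 analysis rule is given there too: "For the primary analyses in Aim 1, we calculate CI's for a single proportion", and the question is whether the benchmark falls inside or outside the interval.

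The section then gives one worked example per hypothesis:

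- H1.2 (at least 50% of eligible people enroll): 357 eligible and 56% enrolled, exact CI 50.7% to 61.2%.
- H1.3 (less than 50% lost): "Assuming that the study loss to follow-up rate is 42%, a sample size of 200 gives a 95% binomial exact confidence interval"; the printed limits are 35.1% and 49.2%.
- H2 (mean completion of at least 70%): "Assuming that the mean percentage of time spent on the training is 73% with a standard deviation (SD) of 15" percent, with 100 in the treatment arm, t interval 70.02% to 75.98%.

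It adds limits for other sample sizes, such as "with 400 people eligible we would only need 55% to enroll". It gives no probability of meeting any benchmark.

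The sample size itself differs between sections. Recruitment via social media plans a 10-week period "to meet our target enrollment of 200 participants (20 participants/week"), which agrees with Sample Size Considerations. Number of Participants has "Number of total participants enrolled (assumes 50% enroll): 400", or 200 per arm, followed by "Number of total participants analyzed (assumes 50% lost to follow-up): 200".

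**The concern.** An observed rate varies around its true value. To show that an interval clears the benchmark when the observed result equals the assumed value is to show where the pass limit lies. It does not show that the sample is large enough to reach that limit reliably. When the assumed value is almost on the limit, the chance of passing cannot be much above one half.

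A reader planning the larger RCT would take n = 200 as adequate for these benchmarks. If an interval then included its benchmark, that could be read as evidence against feasibility, although it was a fairly likely result under the plan's own assumptions. The reader also cannot tell which sample size the statement is about, because the sections disagree on whether 200 or 400 enroll.

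**Working it through.** **Inputs.** All from Sample Size Considerations: 56% of 357 eligible; 42% lost of 200; mean 73%, SD 15%, n = 100; benchmarks 50%, 50% and 70%; two-sided 95% intervals, exact binomial for proportions and t for the mean. From Number of Participants: 400 enrolled, 200 in the intervention arm.

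**Step 1: reproduce the printed intervals.** Exact (Clopper-Pearson) limits for x of n are the beta quantiles B(0.025; x, n − x + 1) and B(0.975; x + 1, n − x).

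- 200/357: 50.70% to 61.24%.
- 84/200: 35.07% to 49.17%.
- 73 ± 1.984 × 15/√100 = 73 ± 2.98: 70.02% to 75.98%.

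All three agree with the plan.

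**Step 2: find the pass limit on the observed value.**

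- H1.2: 197/357 has lower limit 49.86% (fails); 198/357 has 50.14% (passes). The limit is 198 (55.5%); the plan assumes 200.
- H1.3: 85/200 has upper limit 49.67% (passes); 86/200 has 50.17% (fails). The limit is 85 (42.5%); the plan assumes 84.
- H2: 70 + 1.984 × 1.5 = 72.98. The plan assumes 73.00.

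**Step 3: chance of reaching the limit if the assumed value is true.** Exact binomial tails for the proportions. For H2, noncentral t with 99 degrees of freedom and noncentrality (73 − 70)/1.5 = 2.0, which assumes a normal model.

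- H1.2: P(X ≥ 198 | 357, 0.56) = 0.603.
- H1.3: P(X ≤ 85 | 200, 0.42) = 0.586.
- H2: P(T > 1.984) = 0.508.

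**Step 4: how the chance changes with the true value, at the same n.**

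| Hypothesis | True value: chance that the CI clears the benchmark |
|---|---|
| H1.2 (357 eligible) | 56%: 60%; 57.5%: 80%; 58%: 85%; 60%: 96% |
| H1.3 (200 enrolled) | 42%: 59%; 40%: 79%; 39.8%: 80%; 38%: 92% |
| H2 (n = 100, SD 15) | 73: 51%; 74: 75%; 74.25: 80%; 75: 91% |

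**Step 5: the same assumed values with the Number of Participants figures.**

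- H1.3 with 400 enrolled: the limit is 179 lost (upper limit 49.77%; 180 gives 50.02%), and P(X ≤ 179 | 400, 0.42) = 0.878.
- H2 with 200 in the arm: the limit is 70 + 1.972 × 15/√200 = 72.09, and the chance at a true mean of 73 is 0.804.
- H1.2 has no matching figure, because that section gives 800 consented and no number eligible.

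**Footnote on the secondary limits.** Under the exact interval, 220/400 (55.0%) has lower limit 49.98% and 221/400 (55.25%) has 50.23%, so 221 are needed. The quoted loss limits of 40% at n = 150 and 42% at n = 250 satisfy the rule but are stricter than it requires: 62/150 (41.3%, upper limit 49.65%) and 109/250 (43.6%, upper limit 49.99%) still pass.

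**The case against.** The strongest reply is that this is a pilot, that the section names a confidence approach and claims no power, and that its intervals are right. On that view the assumed values are illustrative observed results, and a value near a pass limit gives a chance of 50% to 60% by construction. Much of this stands. A reader might infer that a power calculation was done wrongly; there is none, so that reading fails. What remains is the claim of sufficiency against stated hypotheses under a stated rule, and illustrative limits cannot support it.

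Other parts of the reply also stand:

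- **H2.** The CI is a stated decision rule for Aim 1 only. If H2 is judged by whether the observed mean reaches 70%, the chance at a true mean of 73% is about 98% (3/1.5 = 2 standard errors). The 51% is therefore conditional.
- **Consequences.** The plan attaches no stop or go action to an interval that includes a benchmark, and Study Endpoints rests the conclusion on a mixed methods assessment. A reader might infer that the pilot is set up to fail or that its results are compromised. The documents support neither: the Aim 1 interval will come from the actual data, and odds of about 60 to 40 for H1.2 and H1.3 are not even odds.
- **True values may be better.** Preliminary Studies reports that 85% of eligible people enrolled in the team's earlier study, although that study was cross-sectional.
- **The 55% figure at 400 eligible.** A reader might call it an arithmetic error. The required 55.25% rounds to 55%, the section works in whole percents, and 220/400 passes under a Wilson interval (50.10%) or a Wald interval (50.12%). It is a one-participant rounding matter.

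One-sided 95% bounds, which the plan does not specify, would raise the three chances only to about 72%, 69% and 63%.

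**Conclusion.** The point holds as a minor one. The printed intervals are correct, but the sufficiency they are used to support is not shown. At the plan's own assumed values the Aim 1 rule is met about 60% (H1.2) and 59% (H1.3) of the time, and the H2 interval clears 70% about 51% of the time.

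These figures assume two-sided 95% intervals, 357 eligible and 200 enrolled. For H2 they also assume 100 in the treatment arm, SD 15, a normal model, and that the t interval is the decision rule. With SD 25 the H2 limit at n = 100 would rise to 74.96. H1.1 has no interval in this section and is not covered.

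The conflict between 200 and 400 enrolled is part of the point, since it moves H1.3 from 59% to 88% and H2 from 51% to 80%. The planning loss rate conflicts as well: 42% in Sample Size Considerations, 50% in Number of Participants. A reader might infer from the second figure that H1.3 is expected to fail, because at a true 50% the chance of passing is about 2%. The documents do not say that 50% is the expected rate, and it may be a cautious allowance for recruitment planning.

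**What to change.** 1. Reconcile the enrolled number (200 or 400) across Recruitment via social media, Sample Size Considerations and Number of Participants, and state which loss rate is used for planning and why.
2. In Sample Size Considerations, present the worked values as limits on the observed result, preferably as counts: H1.2 is met with at least 198 of 357 enrolled; H1.3 with at most 85 of 200 lost (at most 179 of 400 if 400 enroll).
3. Replace the sufficiency statement with the chance of meeting the rule at the assumed values and the true values that give about 80%. For n = 200 the chances are 60%, 59% and 51%, and the true values are 57.5% enrolled, 39.8% lost and a mean of 74.25% (SD 15). If 400 enroll, the chances for H1.3 and H2 become 88% and 80%; the remaining figures need recalculation, and H1.2 needs a stated number eligible.
4. State whether the t interval is also the decision rule for H2.
5. In a footnote, give 221 of 400 for the enrollment limit, and 62 of 150 and 109 of 250 for the loss limits.

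Once the sample size is reconciled, this is a matter of wording and a few numbers in one section. Endpoints and the Aim 1 analysis do not change. The downside is that n = 200, if kept, looks less favourable than the present text suggests.

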Protocol and Statistical Analysis Plan

Study Title

Increasing Help-Seeking Behavior Among Transitioning Veterans at Risk for Suicide With Online Gatekeeper Training

Clinical Trials.gov ID

NCT04565951

Date approved by VA Portland Institutional Review Board

06/29/2021

VAPORHCS Research Protocol/Local Protocol Addendum

Title

VAPORHCS/OHSU J: Increasing Help-Seeking Behavior Among Transitioning Veterans At Risk For Suicide With Online Gatekeeper Training: A Pilot Study Of PsychArmor S.A.V.E.

Specific Aims/Purpose

Transitioning Veterans (those who have recently separated from the military) are a high-risk group for suicide. A key component to advancing suicide prevention efforts among at-risk Veterans is to address low levels of help-seeking and engagement in clinical care.

Gatekeeper training is a type of intervention with the potential to substantially increase help-seeking, and thereby contribute to “upstream” suicide prevention efforts. Gatekeeper training teaches individuals the skills needed to identify signs of suicide risk and connect others to professional treatment. PsychArmor S.A.V.E. is a recently-developed form of brief online gatekeeper training and has been tailored to Veterans and their close supports.

We propose to conduct a pilot randomized controlled trial (RCT) of PsychArmor S.A.V.E. Using a targeted advertisement campaign on social media, we will reach and recruit transitioning Veterans and their close supports (family and friends) into this online study. Participants will be randomized 1:1 to PsychArmor S.A.V.E. or to a “sham” online training. We will use a mixed methods evaluation of website administrative data, surveys, and interviews, including follow-up over six months. This pilot will inform a subsequent, larger RCT to determine if PsychArmor S.A.V.E. improves trainee behaviors and reduces rates of suicide behaviors.

Our **Specific Aims** are:

1. **Determine the feasibility of recruiting participants via social media, engaging them to participate in an online gatekeeper training program, and retaining them in an online intervention study.**
2. **Determine the acceptability of PsychArmor S.A.V.E. in a pilot RCT, and evaluate measures for use in a future larger-scale RCT.**

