Veterans' close supports are likely to have the opportunity to intervene on behalf of a Veteran at risk of suicide and seek training in how to help. A study of 971 National Guard personnel found that 65% reported knowing someone who had died by suicide, and on average, participants knew three suicide decedents.⁶ Another study of 931 Veterans found that younger Veterans had an even higher chance of interacting with peers at risk of suicide, suggesting that transitioning Veterans may be an especially good target for suicide prevention efforts.⁷ National data suggest that Americans "overwhelmingly agree they have an important role to play in preventing suicide – and most (78%) are interested in learning how they might be able to play a role in helping someone who may be suicidal."⁸ However, few have ever received training in suicide prevention. Even among groups most often targeted for training (e.g., college students), just 8-10% have had any exposure to training.⁹

Gatekeeper training is a community-based, public health suicide prevention strategy. Gatekeeper training is explicitly designed to provide close supports with training in how to help a person at risk of suicide. It can be delivered outside of the healthcare system, and thus reach Veterans not engaged in VHA care who are most at risk of suicide. Further, it can be useful for both selective and universal prevention.¹⁰ In this proposal we focus on transitioning Veterans—due to their elevated risk for suicide—and their close supports (selective prevention). However, gatekeeper training may also be relevant at a broader population level to support "upstream" suicide prevention (universal prevention).

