- 2) **Outcomes for the recipient of the training.** While the primary goal of training is to equip a close support to help another individual, there is preliminary evidence of an ancillary benefit to the trainee. In post-hoc analyses from a recent RCT, researchers found that recipients of gatekeeper training increased their own mental health care utilization at three months post-intervention.¹² Because close supports for Veterans are often Veterans themselves, exploring the potential benefit of gatekeeper training for the trainee is especially important in a VHA context.

PsychArmor S.A.V.E. is an accessible, engaging, brief online gatekeeper training tailored to the Veteran community. As with all gatekeeper trainings, it teaches practical skills in how to assist a person at risk of suicide and increase formal help-seeking.^{5,12,18} Unlike other gatekeeper trainings (e.g., QPR, Mental Health First Aid, ASIST), though, it is both free and online, which increases its accessibility to Veterans and their close supports.²⁸ PsychArmor S.A.V.E. is also intentionally brief (24 minutes), has a video format, and includes three scripted role plays; these features may help engage individuals who might otherwise be reluctant.²⁵ Finally, it was developed in partnership between VA and the non-for-profit PsychArmor Institute; it is culturally tailored to needs and circumstances of the Veteran community. Cultural tailoring an intervention may improve treatment outcomes, particularly when the population has unique vulnerabilities, and/or when there is a reduced responsiveness to other interventions.²⁹

Social media is an innovative way to reach transitioning Veterans and their close supports, and promote participation in PsychArmor S.A.V.E. Recruitment of participants via social media offers the potential for immediate delivery of an online intervention such as PsychArmor S.A.V.E. Among social media platforms, Facebook is used by most Veterans and has the largest and most active base of users: 76% log on daily and spend on average 50 minutes on the site.³⁰⁻³² Ads on social media platforms such as Facebook have the added benefit of being able to presented to narrowly targeted populations (i.e., “micro-targeting”) based on demographics, location, interests, and behaviors.³³

VA-SPECIFIC REQUIREMENT (relevance to VA mission):

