Qualitative Data Analysis: We will employ qualitative content analysis with a directed grounded theory approach.⁷¹ We have chosen this approach because it will allow us to identify tacit and implicit content in transcripts and use our conceptual framework and theory to guide our initial codebook.⁷² The investigative team (Drs. [name], [name], and [name]) will review the first transcript, discuss general impressions and insights, and develop a preliminary codebook. Full coding of the transcripts will then begin with each transcript being double coded by team members with at least two years’ experience analyzing qualitative data. We will use open coding to add relevant, unexpected, and emergent themes. Conceptual memos to track developing themes and parent/child nodes showing the interrelationship among codes will be created as necessary. Supervised by the investigative team, the coders will review areas of disagreement in coding, develop a consensus, and iteratively refine the codebook as needed. For data management we will use the software program Atlas.ti and use an audit trail to document creation and modification of codes.

Study Endpoints. The study will conclude with an assessment of feasibility and acceptability based on a mixed methods analysis of the quantitative (200 surveys, measures in **Table 2**) and qualitative data (15 interviews) collected. This will contribute towards the design of a larger RCT and may contribute to submission of journal articles for dissemination of findings.

Study Population

Eligibility Criteria. All potential participants will be identified through the targeted social media advertising campaign. After a potential participant clicks on an ad, they will complete a screening that will take place prior to consent. Half of the participants will be randomized to the intervention and half to the control condition. The eligibility criteria are presented in **Table 3** below. Through the targeted social media advertisement campaign, we will recruit recently transitioned veterans (active duty within past 12 months) who have at least weekly social contact with another veteran, and we will recruit friends or family of veterans who have at least weekly social contact with a veteran. Potential participants will be excluded for lacking necessary means of contact for follow-up, lacking fluency in English needed because the

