Because of this, we have opted to provide resources at multiple time points in the study, including the time of consent, and any time in which we would become aware of a subject's positive suicide screen, i.e., when the person is completing the survey instrument (**Appendix B**). Providing resources at that time, rather than conducting risk assessment hours if not days later, is preferable in the context of the current study design. Resources will include information on online, phone, and text messaging-based mental health treatment resources. They will include options for crisis situations, non-urgent treatment referral, and—as we will not be fully aware of the location of respondents—ways to locate local support and treatment resources. Our study team will not provide therapy to directly treat depression or other mental health symptoms for participants who experience distress over the course of the study. We are not limiting participants' engagement with mental health providers in any way.

If a participant indicates they are suicidal during an interview, a warm transfer will be initiated. The interviewer will ascertain that the participant will be available by phone while calling the warm transfer number for the VA National Suicide [contact]). They will provide the participant's name and telephone number to the VA National Suicide Prevention Hotline.

Benefits:

Potential benefits to the individual include the possible acquisition of gatekeeper training skills in suicide prevention for those in the intervention condition. All individuals will also receive information on mental health resources.

This study includes two key potentially important impacts to knowledge of suicide prevention in Veterans. The first impact is the feasibility of the use of social media to provide outreach to Veterans, particularly those who are not VHA connected, and their family and friends. The second impact is the knowledge on the feasibility and acceptability of online training that provides the trainee with the skills to help individuals at risk of suicide. We believe that the knowledge to be gained and the potential benefits from the proposed study outweigh the associated risks.

Protected Health Information:

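### Does admitting family or friends of any Veteran, with no reporting by entry route, undermine a pilot framed around transitioning Veterans?

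*Combined protocol and SAP*

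**What the plan says.** The documents describe the population in two ways.

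**Narrower wording.** The title reads "Increasing Help-Seeking Behavior Among Transitioning Veterans at Risk for Suicide With Online Gatekeeper Training"; it names transitioning Veterans only. The narrative under Specific Aims/Purpose says "we will reach and recruit transitioning Veterans and their close supports (family and friends) into this online study". Scientific Rationale and Significance says "In this proposal we focus on transitioning Veterans—due to their elevated risk for suicide—and their close supports (selective prevention", and later "Social media is an innovative way to reach transitioning Veterans and their close supports, and promote participation in PsychArmor S.A.V.E".

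**Wider wording.** In Table 3, route 1a is a Veteran with active duty in the prior 12 months, and the alternative route is "1b) family member or friend of a Veteran". Criterion 2 asks for weekly contact with a Veteran, not specifically a transitioning one. The text under Eligibility Criteria matches: "we will recruit friends or family of veterans who have at least weekly social contact with a veteran". The Benefits section gives the first expected impact as "feasibility of the use of social media to provide outreach to Veterans, particularly those who are not VHA connected, and their family and friends".

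**Aims and hypotheses.** Aim 1 is to "Determine the feasibility of recruiting participants via social media, engaging them to participate in an online gatekeeper training program" and to retain participants; it names no group. Hypotheses 1.1 to 1.3 and Hypothesis 2 refer to participants, to eligible individuals or to study loss as a whole.

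**Analysis.** Sample Size Considerations sets the benchmarks on pooled numbers. Statistical Analyses plans summaries with the arms combined and by arm. Entry route appears only under Qualitative Interview Sample Considerations, as one characteristic for choosing about 15 interviewees.

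**The concern.** Read against the rationale, route 1b looks too wide. A long-separated Veteran who is a friend of another long-separated Veteran could enter, although the stated reason for the focus is the elevated risk of people who have recently left service. Advertisements may be narrowed to the most cost-effective ones during the campaign, so the mix could move toward whichever route is cheaper to recruit.

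The pilot is meant to inform a larger trial. If the routes differ in enrollment, retention or training completion, pooled benchmarks could be met while one route falls short, and the report might carry no planning values for transitioning Veterans. Enrolled participants could be split afterwards. The Hypothesis 1.2 denominator could not be split if route were not kept for eligible people who do not enroll.

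**Working it through.** **1. The plan's own figures.** Inputs are from Sample Size Considerations. Exact 95% limits for x out of n are Beta(0.025; x, n−x+1) and Beta(0.975; x+1, n−x).

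- Hypothesis 1.2: 200/357 = 56.0%, interval 50.7–61.2%. Stated: 50.7–61.2%.
- Hypothesis 1.3: 84/200 = 42.0%, interval 35.1–49.2%. Stated: 35.1–49.2%.
- Hypothesis 2: 73 ± t(0.975, 99) × 15/√100 = 70.02–75.98. Stated: 70.02–75.98.

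All three reproduce, and all are pooled over entry route.

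**2. What a pooled pass could hide.** The documents give no split between routes and no difference between them, so everything in this step is assumed. Pooled loss is held at 84/200.

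| Route 1a lost | Others lost | Odds ratio | Route 1a interval |
|---|---|---|---|
| 21/40 (52.5%) | 63/160 (39.4%) | (21/19)/(63/97) = 1.70 | 36.1–68.5% |
| 28/40 (70.0%) | 56/160 (35.0%) | (28/12)/(56/104) = 4.33 | 53.5–83.4% |

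For route 1a shares of 10% to 50%, the point estimate passes 50% at odds ratios of 1.7 to 2.1. The whole interval lies above 50% only from 3.8 to 5.2, depending on the share (at a 20% share, 27/40 against 57/160: (27/13)/(57/103) = 3.75). Masking is arithmetically possible, but hiding a clear failure needs a large difference, for which the documents give no evidence.

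**3. What figures by route would show.** The plan's own rates are applied to a route with an assumed share of the sample.

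| Share | Loss to follow-up | Enrollment | Training completion (mean 73, SD 15) |
|---|---|---|---|
| 25% | 21/50: 28.2–56.8% | 50/89: 45.2–66.7% | n = 25: 66.81–79.19 |
| 50% | 42/100: 32.2–52.3% | 100/178: 48.6–63.6% | n = 50: 68.74–77.26 |
| 75% | 63/150: 34.0–50.3% | 150/268: 49.8–62.0% | n = 75: 69.55–76.45 |

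At these shares no interval clears its 50%, 50% or 70% benchmark. Figures by route would be rough planning values, not tests.

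**4. Is the wide criterion a mistake?** Table 3, the Eligibility Criteria text and the Benefits section agree on it. Inclusion of non-Veterans speaks of close supports of Veterans in general, and so does the second paragraph of Scientific Rationale. Intervention Description says the course is tailored to Veterans and their close supports. The title says whose help-seeking should rise, not who is to be trained. The consistent reading is that 1b is intended and the narrower narrative wording is loose.

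**5. Can route be recovered?** For enrolled people, yes. The screener must establish it to decide eligibility, military experiences are collected at baseline, and the team needs the distinction to choose interviewees. For eligible people who do not enroll, Recruitment via social media says REDCap stores the number screened and consented. It does not say that screener answers are discarded. The absence of identifying information in the screener does not prevent route being kept. Appendix B, which holds the screener, is not in the text supplied, so this cannot be settled either way.

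**The case for a change.** The strongest reply is that the plan itself treats the routes as different. It cites slower recruitment in intervention studies that include close supports, samples interviewees by route, and justifies including non-Veterans by the wish to learn how the training works in them. A sampling rule is not a commitment to report, and a trial planned from this pilot would need values for each group. Writing that down would cost one sentence and a few table columns.

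Much of this is fair as advice: a table by route would be useful and cheap. It does not show an error. None of the stated hypotheses is about a route, and nothing in the plan prevents the table.

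The 1a/1b split is also not the obvious one. The rationale notes that close supports are often Veterans themselves, so it would not separate Veterans from non-Veterans, which is the contrast behind the reason given for including non-Veterans. Many 1a entrants, who need weekly contact with another Veteran, could also qualify as that Veteran's friend.

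One could try to give the difference a size from the team's earlier survey, in which 85% of eligible people enrolled. That was a one-off survey of Iraq/Afghanistan-era Veterans averaging 40 years of age. It says little about people within 12 months of active duty entering a randomized trial with six months of follow-up.

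**Conclusion.** The observation is accurate: the narrative wording is narrower than Table 3, and the plan does not commit to results by entry route. No change is needed. Followed as written, the pooled benchmarks give sound answers to the stated aims and hypotheses. The difference in wording is editorial, and a descriptive split of enrolled participants is something analysts can produce from the planned data.

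On size, a route 1a loss estimate above 50% under a pooled pass needs an assumed odds ratio of about 1.7 to 2.1. An interval wholly above 50% needs about 3.8 to 5.2. For a route with 75% of the sample or less, at the plan's own rates, none of the intervals calculated would clear its benchmark.

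This rests on reading route 1b as intended, which several sections support, and on no mix of routes being given. One point stays open: whether the screener's route answer is kept for eligible people who do not enroll. It affects only a possible split of the Hypothesis 1.2 denominator, and the documents do not indicate that the answer is lost.
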